| | Dose, Opioid formulation, number Source (DOSE tool), other analgesics | ALBP, CLBP | ALBP, CLBP | ALBP, CLBP | ALBP, CLBP | CLBP | |
| | Device usage | | ALBP, CLBP | ALBP, CLBP | ALBP, CLBP | CLBP | |
| Sample Size | To estimate the M-Stim | interventi | on effect : | size, a retro | spective st | udy of | |
| | 59 cLBP patients on ch | ronic opioi | ds (100% | prolonged | opioid use) | | |
| | reported a 28% reducti | on in MME | after spin | al stimulat | or | | |
| | implantation,[40] reducing MME 26.2(SD32.8) compared to 5.8(SD34.2) | | | | | | |
| | for those with conventional treatment (effect size 0.60. A priori, we would | | | | | | |
| | be able to detect an effect size of 1 (meaning a difference of 1 standard | | | | | | |
| | deviation) with 94% power and alpha of .03 using a Wilcoxon Mann | | | | | | |
| | Whitney test with 30 in each group. With this effect size for a two-sided | | | | | | |
| | significance of 0.05, 17 participants per group would detect a 30% | | | | | | |
| | prescribing reduction, while 50 participants on chronic opioids per | | | | | | |
| | treatment group would provide 85.4% power to detect a 30% reduction in | | | | | | |
| | MME. Given the 20% in a previous study by Jamieson et al, we increased | | | | | | |
| | the cLBP sample to 50 | - | | Jannoson | icat, we iiio | ioasea | |
| | | | | | | | |

| | We planned to recruit 60 aLBP participants who had never taken opioids for their back pain, and 100 cLBP without a new prescription but with or without chronic opioid for cLBP. |
|----------------------------|--|
| Recruitment | Patients were recruited from Kaizo Health Centers in Landover and Fairfax, through direct referrals, flyers, and digital content like social posts and emails targeting local populations. Flyers were also distributed at three local pain clinics. |
| Randomization | After eligibility screening and informed consent, a 4-digit participant ID and the intervention allocation were randomly assigned by the survey software to either the DuoTherm or LG Smart TENS group within acute and chronic arms. A copy of the informed consent was emailed to the participant. |

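### The sample-size paragraph derives an effect of 0.60, quotes power at an unsourced effect of 1, and gives one 30% label to two different effects, so no stated power is tied to the trial's 30% targets

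*Combined protocol and SAP*

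**What the plan says.** All the power statements are in the Sample Size row of the combined protocol and SAP.

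- The row says its aim is to estimate the M-Stim effect. It uses a study of patients on chronic opioids: "implantation,[40] reducing MME 26.2(SD32.8) compared to 5.8(SD34.2" for stimulator against conventional care, also described as "reported a 28% reducti" (the word is broken in the extracted text). The resulting effect is given as "for those with conventional treatment (effect size 0.60. A priori, we would".
- It goes on: "be able to detect an effect size of 1 (meaning a difference of 1 standard" and "deviation) with 94% power and alpha of .03 using a Wilcoxon Mann", with 30 per group.
- The next sentence opens "Whitney test with 30 in each group. With this effect size for a two-sided" and continues "significance of 0.05, 17 participants per group would detect a 30" per cent reduction in prescribing. It then says that 50 chronic opioid users per "treatment group would provide 85.4% power to detect a 30% reduction in" MME.

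The 30% is the trial's own target. The primary opioid objective is a 30% reduction against TENS. The Outcomes row sets a 30% MME reduction for prior users and a 30% reduction in the proportion of opioid-naïve participants who receive a prescription.

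**The concern.** A reader would expect the power to be given at the effect just derived, or to be told why another was chosen. The paragraph instead moves from 0.60 to 1, about two-thirds larger, without a reason. It then uses one phrase, this effect size, to introduce two figures that cannot share an effect, and calls both a 30% reduction.

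The trial has finished enrolling, so what is at stake is interpretation. With 94% on record beside 30 per group, and 60 acute participants planned, a null acute result could be read as strong evidence of no benefit. With 85.4% labelled as power for a 30% MME reduction, a reader would take the primary opioid objective as the effect that was powered. The paragraph supports neither reading.

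**Working it through.** **Inputs (Sample Size row).** Mean MME reductions 26.2 (SD 32.8) and 5.8 (SD 34.2); 28% reduction; 30 per group at alpha 0.03 by Wilcoxon-Mann-Whitney; 17 and 50 per group at two-sided alpha 0.05. The row does not say whether the 0.03 is two-sided. It is taken as two-sided, which reproduces the stated power.

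**Method.** Two-sample noncentral t power. For the Wilcoxon test, n is multiplied by the asymptotic relative efficiency 3/π (30 becomes 28.6).

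**Step 1: the derived effect.** The difference is 26.2 − 5.8 = 20.4 MME. The pooled SD is √((32.8² + 34.2²)/2) = 33.5. So d = 20.4/33.5 = 0.609. The stated 0.60 is rounding or a different choice of SD (20.4/34.2 = 0.596) and does not matter here.

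**Step 2: which effect reproduces each stated figure.**

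| Stated figure | At d = 1 | At d = 0.609 |
|---|---|---|
| 94%, 30 per group, alpha 0.03, Wilcoxon | 93.7% (simulation 93.7%) | 53% (t-test 56%) |
| 17 per group, alpha 0.05, t-test (power not stated) | 80.7% (16 per group: 78.1%) | 41% |
| 85.4%, 50 per group, alpha 0.05, t-test | 99.9% | 85.41% |

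The 94% is a 1-SD figure. The 17 is the smallest group size reaching the conventional 80% at 1 SD in a continuous outcome. The 85.4% is the power for the 20.4 MME benchmark difference. The two figures that share the 30% label therefore use 1 SD and 0.609 SD.

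**Step 3: what 30% would be in MME.** The documents give no baseline MME. Assume that 26.2 MME and 28% describe the same arm and starting level. Then:

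- Baseline = 26.2/0.28 = 93.6 MME, and 20.4/93.6 = 21.8%.
- A 30% difference from control is 0.30 × 93.6 = 28.1 MME, d = 28.1/33.5 = 0.84, and power with 50 per group is 98.6%.
- A 30% fall in the M-Stim arm against the benchmark control fall is 28.1 − 5.8 = 22.3 MME, d = 0.66, and power is about 91%.

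The percentage depends wholly on the baseline. At 20.4/0.30 = 68 MME, the same 20.4 MME would be exactly 30%, although 68 MME does not fit the shared-baseline reading.

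**Step 4: the acute primary outcomes.** These are receipt of a prescription (binary) and NRS pain at 10 days. No calculation in the row uses a proportion or an NRS SD. As an illustration only, take the 25% national comparator as the control prescribing rate. A 30% relative reduction (25% to 17.5%) then has about 8% power with 17 per group and about 10% with 30. Reading 30% as 30 percentage points, with assumed control rates from 30% to 100%, gives about 42% to 71% with 17 per group and 65% to 92% with 30.

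**The case against.** **There is no calculation error.** This stands. Both stated powers reproduce, and the 94% sentence names its own condition, a 1-SD difference. The fault lies in which effects were chosen and how they were labelled.

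**A reader might infer that the acute part has only about 53% power.** The documents do not support that. The 0.609 is an MME reduction in chronic opioid users. The planned acute participants had never taken opioids for their back pain, so they have no such MME to reduce, and their primary outcomes are of another kind. The row also does not say which stratum or outcome the 1-SD sentence serves. The link to the 60 acute participants is only that 60 is twice 30, and the amendment history attributes the increase to 60 and 100 to FDA recommendations. The 53% is the power for an MME difference of 0.61 SD with 30 per group and nothing more.

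**A reader might infer that 85.4% overstates the power for 30%.** It does not on the only baseline that can be worked out from the text, where power for 30% would be higher. Nor can 22% be stated as a fact, since it rests on a baseline the documents do not give. The 28% within-arm fall is also near the 30% in the prior-use outcome, which may explain the label. But that is a fall within one arm, whereas 85.4% is the power for a difference between arms.

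**The text of this row is damaged.** A bracket is left open after 0.60, and the noun after a later 20% is missing. A lost linking phrase cannot be excluded, but the quoted sentences are readable and step 2 rests on numbers that survived intact.

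**Conclusion.** The point holds as one of choice and labelling of effects. The paragraph derives 0.60, moves to an unsourced effect of 1, and calls both a 1-SD effect (17 per group) and a 0.609-SD effect (50 per group) a 30% reduction. Because 30% is never expressed in MME or SD, no stated power is shown to belong to the 30% targets in the Objectives and Outcomes rows.

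For an MME outcome with 30 per group at two-sided alpha 0.03, power is about 53% at the effect the paragraph derived, against 94% at the effect it used. For 50 opioid users per group, 85.4% is correct for 20.4 MME and mislabelled as 30%. Under the shared-baseline assumption it is conservative for a true 30% effect (91% to 98.6%). For the acute primary outcomes the paragraph gives no valid power, so neither 94% nor 53% should be attached to them.

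These results assume roughly normal outcomes with the benchmark SDs and equal groups. They also take the row's condition that all 50 per group use opioids. Whether the enrolled chronic participants meet it is a separate question.

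**What to change.** Restate the power sentences so that each names its effect, alpha and type of outcome. For example:

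- 30 per group gives 94% power for a 1-SD difference at alpha 0.03 (Wilcoxon), and about 53% for an MME difference of 0.61 SD, the effect derived from the benchmark.
- 17 per group gives about 80% power for a 1-SD difference in a continuous outcome at two-sided alpha 0.05.
- 50 opioid users per group gives 85.4% power for a 20.4 MME (0.61 SD) difference at two-sided alpha 0.05.

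Give the source of the 1-SD effect, or say that it was a detectable-effect choice. Remove the 30% label from these sentences, or define it by the baseline MME, difference and SD it stands for. State that no power was calculated for receipt of a prescription or for NRS pain at 10 days, and do not cite 94% when interpreting a null acute result.

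The cost is wording only, with no extra patients and no change of analysis. The downside is that the acute part loses the 94% figure and its stated power looks less favourable.

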| Roles and Responsibilities | Principal Investigator: [name] MD, responsible for study design, overall project oversight, and compliance. Study Coordinator: [name], responsible for daily operation, protocol adherence and patient coordination at Kaizo Health Centers. [name] assisted [name] with initial study design, ongoing recruitment recommendations, pain measure decision-making, study flow creation. [name] PhD (Deceased), responsible for initial power analysis, statistical support for study design, revisions after FDA. [name] PhD, responsible for programming of data collection instruments, ongoing support of data collection tool and dataset, database consolidation; [name] PhD, responsible for statistical analysis of completed dataset. All apart from [name] reviewed the manuscript. |
| Introduction | Low back pain (LBP) affects nearly 40% of adults, contributing to significant reductions in quality of life and productivity. The opioid epidemic, largely driven by prescriptions for pain, has created an urgent need for effective non-pharmacological pain treatments. Existing options such as TENS devices may provide acute relief, but are not available as an opioid substitute. A multimodal approach, combining mechanical stimulation, heat, cold, and acupressure, holds promise for reducing both acute and chronic pain and opioid prescribing. |
| Background and rationale for the study | Between 25 and 50% of patients presenting with acute or exacerbated chronic LBP (a/cLBP) receive prescriptions for opioids. ALBP progresses to chronic in 40% of those with moderate to severe pain (4 out of 10 on a 0 – 10 Numeric Rating Scale). Opioid pain relief is no better than placebo at 6 weeks after presentation, but increases the risk of cLBP and persistent use (5% of opioid naïve). Providing a multimodal low back pain device could reduce opioid prescribing or use compared to TENS; providing any device could reduce opioid prescribing and use compared to contemporaneous prescribing practices. |
| Objectives | Primary Objective, Opioids: To determine whether the use of a multimodal neuromodulatory mechanical stimulation (M-Stim) device (DuoTherm) can reduce opioids 30% compared to TENS in those with moderate to severe back pain. |

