| | Participants will be instructed to use the device for a minimum of 30 minutes a day. Both M-Stim and LG Smart TENS groups will receive a standard pain management regimen typically used for low back pain standardized across all clinicians participating in the study. Participants will keep the devices and be instructed to use them for pain as needed during the duration of the study. |
| Outcomes | Opioid Use Primary Outcome: |
| | Prior use: For patients with prior or ongoing opioid use, a 30% reduction in MME (Milligram Morphine Equivalents) between the first 14 days and the last 14 days of daily diary recordings using the DOSE data collection tool. |
| | Opioid naïve: 30% reduction of those receiving an opioid prescription "prescribed to me for this event" |
| | Secondary outcomes: Use days; total MME and use past 7 days in the opioid naïve; use days by those with more severe pain using the NIH Research Taskforce definitions; and prescribing compared to a contemporaneous national LBP population (25%). |
| | Pain Primary Outcome: |
| | Chronic: 30% lower disability at 6 months using PROMIS Pain Interference for those with ongoing pain >3 months |
| | Acute: 30% lower NRS 0-10 "pain now" from entry to 10 days for those presenting with an episode of pain starting within the past 2 weeks |
| | Secondary Outcomes: Change in disability for those with >=57.7 PROMIS Pain Interference; restoration of function to normal (PI=50); |

| | integrated analysis with | n common | criteria fo | r restoration | on of function | on with | |
|-------------------------|---|---------------|--------------------|---------------------|----------------------|----------------------------|--|
| | multifidus stimulation s | surgery. | | | | | |
| | | | | | | | |
| Participant Timeline | | Initial Visit | Daily x 28 days | Weekly for 3 months | Monthly for 3 months | Monthly 4 - 6 months | |
| | Consent, Enrollment, Randomization | ALBP, CLBP | | | | | |
| | Minimum Dataset, Pain Catastrophizing Sullivan, PROMIS Depression, Physical Function | ALBP, CLBP | | | | | |
| | NRS (at that moment & past 24 hours) | ALBP, CLBP | ALBP, CLBP | ALBP, CLBP | ALBP, CLBP | CLBP | |
| | NRS after 30 minutes | ALBP, CLBP | | | | | |
| | NRS Past week | | | ALBP, CLBP | ALBP, CLBP | CLBP | |
| | NRS Past month | | | | ALBP, CLBP | CLBP | |
| | PROMIS Pain Intensity, Pain Interference | ALBP, CLBP | | ALBP, CLBP | ALBP, CLBP | CLBP | |

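### The 17 per group said to detect a 30% prescribing reduction is not supported for a yes/no outcome: the effect size is in SD units, and no power, TENS-arm rate or meaning of 30% is given

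*Combined protocol and SAP*

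**What the plan says.** All of the sizing is in the Sample Size section. It first gives an effect size of 0.60 from an earlier spinal-stimulator study: MME reductions of 26.2 (SD 32.8) and 5.8 (SD 34.2). It then says the trial would "be able to detect an effect size of 1 (meaning a difference of 1 standard" deviation), with 94% power and alpha .03, by a Wilcoxon Mann-"Whitney test with 30 in each group. With this effect size for a two-sided" "significance of 0.05, 17 participants per group would detect a 30" per cent prescribing reduction. The same sentence adds that 50 participants on chronic opioids per "treatment group would provide 85.4% power to detect a 30% reduction in" MME. The recruitment target follows: "We planned to recruit 60 aLBP participants who had never taken opioids" for their back pain, plus 100 chronic participants.

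In Outcomes, the opioid-naive primary outcome is a "30% reduction of those receiving an opioid prescription" for the event, so each participant either has one or does not.

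Prescribing rates appear in two places, neither tied to the sample size. Background and rationale has "Between 25 and 50% of patients presenting with acute or exacerbated chronic LBP" receiving opioid prescriptions. Among the secondary outcomes is "prescribing compared to a contemporaneous national LBP population (25" per cent). Statistical Methods reports prescribing both as a percentage change and as a relative risk, so it does not settle which kind of 30% is meant.

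**The concern.** Power for two proportions depends on both rates. A standardised mean difference fixes neither of them. Without a TENS-arm rate and a scale for the 30%, the 17 cannot be derived from the plan, and without a stated power it is unclear what detecting the reduction means.

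The two readings of 30% are also far apart. From a rate of 50%, a relative 30% reduction ends at 35%, and a 30-point reduction ends at 20%. From 25%, the first ends at 17.5% and the second cannot occur.

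This is the only sizing statement for prescribing, which is a primary outcome. A reader who takes 17 per group as adequate could read a non-significant result at a somewhat larger number as good evidence of no difference.

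**Working it through.** **Inputs.** From Sample Size: 17 per group, two-sided 0.05; effect sizes 1 SD and 0.60; 50 per group with 85.4% power; 60 acute participants. My assumptions: 1:1 allocation (so 30 per group planned); TENS-arm rates of 25-50%, borrowed from the background range; an uncorrected chi-square test, with Fisher's exact test in brackets.

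**1. The plan's own figures.** The effect size from the stated means and SDs is (26.2 − 5.8)/√[(32.8² + 34.2²)/2] = 20.4/33.5 = 0.609. For a two-sample t-test at two-sided 0.05:

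- 50 per group, d = 0.609: power 85.4%, the stated figure.
- 50 per group, d = 1: power 99.9%.
- 17 per group, d = 1: power 80.7%; 80% power needs 16.7 per group.
- 17 per group, d = 0.609: power about 41%.

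So the 85.4% goes with d = 0.609. If the 17 goes with d = 1, one phrase covers two effect sizes within one sentence. The match of 17 to a t-test depends on a power of 80% that the plan does not state. The test the section names, Wilcoxon Mann-Whitney, gives about 78% at 17 per group for d = 1 (by simulation).

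**2. Power for a yes/no outcome at 17 per group.** With x and y prescriptions among n per arm and p̄ = (x + y)/2n, the statistic is X² = [(x − y)/n]² / [p̄(1 − p̄)(2/n)], and the test rejects when X² ≥ 3.84. Power is the sum of Bin(x; n, p₁) × Bin(y; n, p₂) over all rejecting pairs.

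| Reading of 30% | TENS rate → M-Stim rate | Chi-square (Fisher) |
|---|---|---|
| Relative | 25% → 17.5% | 7.6% (3.7%) |
| Relative | 50% → 35% | 15.3% (8.3%) |
| 30 points | 50% → 20% | 45.6% (31.9%) |
| 30 points | 35% → 5% | 63.0% (48.0%) |
| 30 points | 30% → 0% | 79.8% (61.1%) |
| 30 points | 25% | impossible |

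The 30% → 0% row can be checked by hand. With y = 0, x = 3 gives X² = 3.29 and x = 4 gives 4.53, so rejection needs x ≥ 4, and P[Bin(17, 0.30) ≥ 4] = 0.798.

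**3. The planned 30 per group.** By the same method:

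- Relative 30%: 10.6% (6.0%) from 25%; 21.7% (14.8%) from 50%.
- 30 points: 69.2% (59.6%) from 50%; 88.0% (78.8%) from 35%; 99.1% (92.3%) from 30%.

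**4. Precision at 30 per group.** For an observed relative risk of 0.70, SE(log RR) = √[(1 − p₁)/(np₁) + (1 − p₂)/(np₂)]. The 95% CI is 0.26 to 1.89 with a 25% TENS rate and 0.38 to 1.28 with 50%.

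**The case against.** The strongest reply is that 30% means 30 points and that 17 is then nearly right. In the most favourable case within the assumed range, 30% falling to zero, exact chi-square power is 79.8%, and one more participant per group takes it past 80%. There is even a binary route to 17: the arcsine effect size for 31% against 1% is 0.981, and 2 × [(1.96 + 0.842)/0.981]² = 16.3. This stands as a possibility. It does not justify the figure: the plan gives neither those rates nor that method, exact power at 31% against 1% is 75.8% (58.1%), and either case needs almost no prescribing on M-Stim.

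It is also fair that the chi-square test is partly my assumption. Statistical Methods names it for summary comparisons and gives percentage change and relative risk for prescribing. Fisher's test lowers every figure.

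A reader might infer two stronger things. One is that the 17 is known to be a t-test calculation for 1 SD at 80% power, wrongly transferred to a proportion. The arithmetic fits, but the documents do not name that test or power for the 17, and the named Wilcoxon test falls slightly short, so this remains an inference. The other is that the trial was sized at 17 per group. It was not: 60 acute participants were planned, about 30 per group.

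**Conclusion.** The point holds as a minor one. The 17 per group is not supported for the proportion it is meant to size. Across the assumed TENS-arm rates of 25-50%, no case examined reaches 80% power by chi-square under either reading of 30%. What the plan can claim at its actual target depends almost wholly on the undefined 30%: at 30 per group, power is 11-22% if it is relative, and 69-99% if it is 30 points from TENS rates of 50% down to 30%.

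These figures rest on 1:1 allocation, two-sided 0.05 and a TENS-arm range that the plan does not state for this trial. The harm is confined to how a result is read, because the 17 did not set the planned size and enrolment is complete.

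**What to change.** - Annotate the sentence: the 17 per group is not supported for a yes/no outcome. Do not assert where the number came from.
- State whether 30% is relative or in percentage points, and give the assumed TENS-arm rate, taken from outside the trial's own results.
- Restate two-proportion power at the planned 30 per group, marked as added after enrolment, by chi-square (Fisher): relative 30% from 25-50%, 11-22% (6-15%); 30 points, 69% (60%) from 50%, 88% (79%) from 35%, 99% (92%) from 30%, not possible from 25%.
- Report the planned percentage change and relative risk with 95% confidence intervals, and do not read non-significance as no difference.

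The cost is one annotation, one definition, one power sentence and the intervals. No extra enrolment is proposed. The stated sizing becomes less favourable.

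### The 85.4% power for the prior-use MME primary assumes 50 chronic opioid users per arm, a count that the recruitment plan does not secure

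*Combined protocol and SAP*

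**What the plan says.** The opioid primary outcome for prior users is defined under Outcomes: "For patients with prior or ongoing opioid use, a 30% reduction in MME" between the first and last 14 days of the daily diary. The primary objective makes this a comparison with TENS.

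The Sample Size section takes its effect from a retrospective study of 59 chronic back pain patients, all on prolonged opioids: "implantation,[40] reducing MME 26.2(SD32.8) compared to 5.8(SD34.2", with the effect size given as 0.60. It next says the trial would "be able to detect an effect size of 1 (meaning a difference of 1 standard" deviation, using a Wilcoxon-Mann-Whitney test with 30 per group. One sentence then gives two further results, 17 per group for a prescribing reduction and the MME power: "prescribing reduction, while 50 participants on chronic opioids per" "treatment group would provide 85.4% power to detect a 30% reduction in" MME.

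Recruitment is described at the end of the section. For the acute stratum: "We planned to recruit 60 aLBP participants who had never taken opioids for their back pain". For the chronic stratum: "100 cLBP without a new prescription but with or without chronic opioid for cLBP". Eligibility Criteria likewise admit chronic patients whether or not they take opioids, and exclude acute patients only for opioid use in the current exacerbation. Randomization is within the acute and chronic strata; opioid use is not a factor.

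Statistical Methods applies the paired first-versus-last-two-weeks MME test to participants who used opioids during the study. A stratification note under Protocol Amendments, written after enrolment, reports that half of each stratum had no prior opioids for low back pain and that the data were pooled.

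**The concern.** The power statement needs 100 opioid users, 50 in each arm. The plan supplies 100 chronic participants who need not be users. The two counts agree only if everyone in the chronic stratum contributes to the MME outcome, and nothing legible in the plan makes that happen or says it was expected.

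A reader will take 85.4% as the power of a primary comparison with TENS. If the number of users is well below 50 per arm, a null MME result could be over-read as evidence of no difference.

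A second obstacle is that the basis of the figure is hard to identify. The sentence opens with a reference back to an effect size ("Whitney test with 30 in each group. With this effect size for a two-sided"), and the nearest one is 1, attached to a rank test. The 85.4% does not come from that effect size.

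**Working it through.** **Inputs.** Mean MME reductions 26.2 (SD 32.8) and 5.8 (SD 34.2), two-sided 0.05, 50 users per group, 100 chronic and 60 acute planned (all from Sample Size). Allocation ratio not stated; 1:1 assumed.

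**Step 1: reproduce the plan's figure.**
- Difference = 26.2 − 5.8 = 20.4.
- Pooled SD = √[(32.8² + 34.2²)/2] = √1122.74 = 33.51.
- d = 20.4/33.51 = 0.609.
- Two-sample t-test with n per arm: noncentrality d√(n/2), 2n − 2 degrees of freedom. At n = 50 the noncentrality is 0.609 × 5 = 3.04 and the power is 85.4%, matching the plan.
- A Wilcoxon-Mann-Whitney test, assuming 0.955 relative efficiency, gives 83.8% at n = 50.

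**Step 2: which effect size is behind it.** At n = 50, d = 1 would give 99.9%, so the 85.4% rests on d = 0.61. The 17 per group in the same sentence behaves the other way: a two-sample t-test at two-sided 0.05 gives 80.7% with d = 1 and only 41% with d = 0.61. One sentence therefore mixes two effect sizes.

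**Step 3: power by users per arm** (t-test, d = 0.609, two-sided 0.05).

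| Users per arm | Share of 50 chronic per arm | Power |
|---|---|---|
| 50 | 100% | 85.4% |
| 44 | 88% | 80.6% |
| 40 | 80% | 76.7% |
| 30 | 60% | 64.0% |
| 25 | 50% | 55.9% |
| 20 | 40% | 46.7% |

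If only the chronic stratum supplies users, 80% power needs about 44 per arm, an 88% share.

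**Step 4: illustration with the post-enrolment half share, on planned numbers.**
- Chronic stratum only: 100 × 0.5/2 = 25 per arm, 55.9%.
- Both strata pooled: (100 + 60) × 0.5/2 = 40 per arm, 76.7%.
- Share needed for 50 per arm: 100/100 = 100% from the chronic stratum, or 100/160 = 62.5% if both strata contribute.
- Effect detectable with 85.4% power: d = 0.61 at 50 per arm, 0.68 at 40 and 0.87 at 25, or about 20, 23 and 29 MME at SD 33.5.

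The power of the paired tests and relative risks in Statistical Methods is not computed here.

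**The case against.** **The condition is already stated.** The sentence itself says that the 50 are on chronic opioids. That is true. What is absent is any link between that condition and the people to be recruited, and the next paragraph says they need not meet it.

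**A damaged sentence may explain the 50.** The text after the power statement refers to 20% in a previous study and to raising the chronic sample to 50, but it is broken in extraction and the 20% has no noun. It might be attrition, an opioid-use rate or something else. This stands: one can say only that the legible text gives no user share, and the sentence cannot be relied on either way.

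**The half share is weak evidence of the user count.** This also stands. It was seen after enrolment and concerns opioids for low back pain only. The outcome covers prior or ongoing use without that limit, and the diary tool records opioids prescribed for another event, so the count could be higher than half. It could also be lower, because prior users may have taken none during the study.

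**The effect size may not carry over.** The 0.61 comes from patients who were all on prolonged opioids. Prior users who are not on chronic opioids may have little MME to reduce. This limits the smaller powers above, but it gives no support to applying 85.4% to a mixed population.

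**The protocol already discloses the half share and the pooling, and a table made now could look like retrospective power.** That is a fair caution. It is met by leaving the planning figure visible and labelling the other values as illustrative.

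**Conclusion.** The 85.4% is correct for 50 participants on chronic opioids per group, but the plan does not secure that count. With the acute stratum planned as never having taken opioids for back pain, the figure describes this trial only if essentially all chronic enrolees are users. The acute eligibility rule is looser than that description, so some prior users could come from that stratum; 50 per arm would then need 62.5% users among all 160.

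A reader might infer three stronger things that the documents do not support:
- That 85.4% was miscalculated. It reproduces exactly.
- That the trial's actual power was 56% or 77%. Those values apply a post-enrolment share to planned numbers, keep d = 0.61 and assume 1:1 allocation. The number of users analysed is not given, and the values are not the power of the paired tests.
- That more participants should be enrolled. Enrolment is complete, and the fault lies in what the power statement conveys.

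This should be fixed, because it concerns the stated power of a primary outcome and the correction is cheap.

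**What to change.** Revise the Sample Size paragraph as follows.

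1. Keep the 85.4% visible as the planning figure. State that it rests on d = 0.61 (20.4/33.5 MME) with a two-sample t-test at two-sided 0.05, and that the 17-per-group figure in the same sentence fits an effect size of 1.
2. State that the 100 chronic recruits were not required to be opioid users. Give the user share assumed at planning, or say that none was assumed. Restore the sentence on the 20% in legible form, saying what the 20% is.
3. Add power by number of opioid users per arm, on the same d and test: 50, 85%; 44, 81%; 40, 77%; 30, 64%; 25, 56%; 20, 47%. Label these as illustrative, note that d = 0.61 comes from patients all on prolonged opioids, and say that they are not the power of the paired tests in Statistical Methods.

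The cost is one paragraph, with no new data and no extra enrolment. The downside is a less favourable stated power.
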